## 10. MEASUREMENT OF EFFECT

Although response is not the primary endpoint of this trial, participants with measurable disease will be assessed by RECIST (1.1) for soft tissue progression, PCWG-2 (2008) for bone disease progression, bone scan and PSA criteria. For the purposes of this study, participants will be evaluated every four weeks by PSA and every 12 weeks by CT and bone scan. Participants should not be taken off treatment until documented symptomatic progression or progression by imaging.

The following will be used to determine progression in this study:

- **PSA Progression:** For those who experience a decline on PSA from baseline, PSA progression will be defined as an increase in PSA that is  $\geq 25\%$  and  $\geq 2$  ng/mL above nadir which is confirmed by a second value three or more weeks later. For participants who do not experience a decline from baseline, PSA progression will be defined as PSA  $\geq 25\%$  and  $\geq 2$  ng/mL after 12 weeks.
- **Radiographic Disease Progression:** For bone disease, radiographic progression will be defined as the appearance of  $\geq 2$  new lesions on bone scan. For soft tissue/lymph node disease, radiographic progression will be defined using RECIST 1.1 criteria. PCWG-2 (2008) will be used to define bone disease progression.
- If any of the following criteria that are also described in Section 5.4 are met:
  - Symptomatic or radiographic disease progression
  - Intercurrent illness that prevents further administration of treatment
  - Unacceptable AE(s)
  - Treatment emergent seizure
  - Participant decided to withdraw from the study
  - General or specific changes in the participant's condition render the participant unacceptable for further treatment in the opinion of the treated investigator.

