### 10.1 Antitumor Effect– Solid Tumors

Response and progression will be evaluated in this study using the new international criteria proposed by the RECIST 1.1.

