#### 10.1.4 Response Criteria

##### 10.1.4.1 Evaluation of Target Lesions

Complete Response (CR): Disappearance of all target lesions. Any pathological lymph node must have reduction in short axis to < 10 mm.

Partial Response (PR): At least a 30% decrease in the sum of the diameters of target lesions, taking as reference the baseline sum diameters.

Progressive Disease (PD): At least a 20% increase in the sum of the diameters of target lesions, taking as reference the smallest sum on study with at least a 5 mm absolute increase in the sum of all lesions. The appearance of one or more new lesions\* denotes disease progression.

Stable Disease (SD): Neither sufficient shrinkage to qualify for PR nor sufficient increase to qualify for PD, taking as reference the smallest sum diameters while on study.

Unknown (UN): Assessment of target lesions cannot be made due to insufficient or unevaluable data. In this case, a concise explanation must be given.

**Note:** If tumor response data is missing for target lesions, the overall assessment must be UN unless there is new disease that would result in an overall assessment of PD. However, if there is missing or unevaluable data for non-target lesions, but data is available for all target lesions, the overall response for that time point will be assigned based on the sum LD of all target lesions. Additionally, the assessment of CR cannot be made if there is missing or unevaluable data for non-target lesions. In this case, the overall assessment would be PR.

CONFIDENTIAL

This document is confidential. Do not disclose or use except as authorized.

**\*Definition of New Lesion:** The finding of a new lesion should be unequivocal (i.e. not due to difference in scanning technique, imaging modality, or findings thought to represent something other than tumor (ex: new bone lesions may be healing or flare of pre-existing lesions). However, a lesion identified on a follow-up scan in an anatomical location that was not scanned at baseline is considered new and will indicate PD. If a new lesion is equivocal (because of small size, etc.), follow-up evaluation will clarify if it truly represents new disease and if PD is confirmed, progression should be declared using the date of the initial scan on which the lesion was discovered.

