#### 10.1.4.2 Evaluation of Non-Target Lesions

Complete Response (CR): Disappearance of all non-target lesions and normalization of tumor marker level. All lymph nodes must be non-pathological in size (< 10 mm short axis).

**Note:** If tumor markers are initially above the Institutional ULN normal limit, they must normalize for a subject to be considered in complete clinical response.

Non-CR/Non-PD: Persistence of one or more non-target lesions and/or maintenance of tumor marker level above the normal limits.

Progressive Disease (PD): Appearance of one or more new lesions and/or unequivocal progression of existing non-target lesions.

When the participant also has measurable disease, to achieve ‘unequivocal progression’ on the basis of the non-target disease, there must be an overall level of substantial worsening in non-target disease such that, even in presence of SD or PR in target disease, the overall tumor burden has increased sufficiently to merit discontinuation of therapy. A modest ‘increase’ in the size of one or more non-target lesions is usually not sufficient to qualify for unequivocal progression status. The designation of overall progression solely on the basis of change in non-target disease in the face of SD or PR of target disease will therefore be extremely rare. When the participant has only non-measurable disease, worsening in non-target disease cannot be easily quantified. A useful test that can be applied when assessing non-targets for unequivocal progression is to consider if the increase in overall disease burden based on the change in non-measurable disease is comparable in magnitude to the increase that would be required to declare PD for measurable disease: i.e. an increase in tumor burden representing an additional 73% increase in ‘volume’

CONFIDENTIAL

This document is confidential. Do not disclose or use except as authorized.

(which is equivalent to a 20% increase diameter in measurable lesions), an increase in pleural effusion from ‘trace’ to ‘large’, an increase in lymphangitic disease from ‘localized’ to ‘widespread’.

Unknown (UN): Assessment of non-target lesions cannot be made due to insufficient or unevaluable data. In this case, a concise explanation must be given.

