#### For Participants with Measurable Disease (i.e., Target Disease)

Target Lesions	Non-Target Lesions	New Lesions	Overall Response	Best Overall Response for when Confirmation is Required:
CR	CR	No	CR	≥4 wks confirmation
CR	Non-CR/Non-PD	No	PR	≥4 wks confirmation
CR	Not evaluated	No	PR	
PR	Non-CR/Non-PD/Not evaluated	No	PR	
SD	Non-CR/Non-PD/Not evaluated	No	SD	Documented at least once ≥4 wks from baseline
PD	Any	Yes or No	PD	No prior SD, PR or CR
Any	PD*	Yes or No	PD	
Any	Any	Yes	PD	

CONFIDENTIAL

This document is confidential. Do not disclose or use except as authorized.

\* In exceptional circumstances, unequivocal progression in non-target lesions may be accepted as disease progression.

Note: Participants with a global deterioration of health status requiring discontinuation of treatment without objective evidence of disease progression at that time should be reported as "*symptomatic deterioration*". Every effort should be made to document the objective progression even after discontinuation of treatment.

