**For Participants with Non-Measurable Disease (i.e., Non-Target Disease)**

Non-Target Lesions	New Lesions	Overall Response
CR	No	CR
Non-CR/non-PD*	No	Non-CR/non-PD*
Not all evaluated	No	Not evaluated
Unequivocal PD	Yes or No	PD
Any	Yes	PD
*Non-CR/non-PD is preferred over stable disease for non-target disease since SD is increasingly used an endpoint for assessment of efficacy in some trials so to assign this category when no lesions can be measured is not advised.		

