10.1.5 Duration of Response

Duration of overall response: The duration of overall response is measured from the time measurement criteria are met for CR or PR (whichever is first recorded) until the first date that recurrence or progressive disease (PD) is objectively documented, taking as reference for PD the smallest measurements recorded since the treatment started, or death due to any cause. Participants without events reported are censored at the last disease evaluation.

Duration of overall complete response: The duration of overall CR is measured from the time measurement criteria are first met for CR until the first date that recurrent or progressive disease is objectively documented, or death due to any cause. Participants without events reported are censored at the last disease evaluation.

Duration of stable disease: Stable disease is measured from the start of the treatment until the criteria for progression are met, taking as reference the smallest measurements recorded since the treatment started.

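### Section 10 needs two or more new bone-scan lesions for bone progression, but the Section 10.1.4 response rules call one unequivocal new lesion PD, and nothing says which governs response and its duration.

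*Combined protocol and SAP*

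**What the plan says.** Section 10 divides the assessment by site. Soft tissue and lymph nodes go to RECIST 1.1 and bone goes to PCWG-2. The bone rule reads "For bone disease, radiographic progression will be defined as the appearance of" at least two new lesions on bone scan.

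Section 10.1 opens without that division: "Response and progression will be evaluated in this study using the new international criteria proposed by the RECIST 1.1". Two rules follow:

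- Section 10.1.4.1 (target lesions): "The appearance of one or more new lesions" is PD.
- Section 10.1.4.2 (non-target lesions): PD is "Appearance of one or more new lesions and/or unequivocal progression of existing non-target lesions".

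The note defining a new lesion requires the finding to be unequivocal and gives as an example of what to set aside that "new bone lesions may be healing or flare of pre-existing lesions". It sets no minimum number of lesions. Both overall-response tables in 10.1.4.3 (measurable and non-measurable disease) return PD for any new lesion, whatever the status of existing disease.

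Under 10.1.5, response lasts "until the first date that recurrence or progressive disease (PD) is objectively documented", or until death. Section 1.3 lists response of measurable disease and its duration as secondary objectives. Section 14.2 describes duration by Kaplan-Meier and uses RECIST response to form groups for exploratory comparisons of the resistance measures.

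**The concern.** One finding, a single genuine new lesion on bone scan, gets two answers. Section 10 says the participant has not progressed. The 10.1.4 tables say PD. No sentence ranks the two rules or confines the one-lesion rule to soft tissue.

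What is at stake is the date on which some responses end and, in a narrower set of cases, whether a participant counts as a responder at all. Section 10.1.7 plans central radiology review, which should make readings consistent across sites, but it does not say which rule the central readers apply to response.

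**Working it through.** The plan states no figure that depends on this point, so there is none to reproduce. The check is to apply both rules to the same cases.

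**Cases.** Take a participant with target status CR, PR or SD, no new soft-tissue lesion and no progression of existing lesions. Any new bone-scan lesions are unequivocal and not flare or healing.

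| New bone-scan lesions | Section 10 | Section 10.1.4 tables |
|---|---|---|
| 0 | not progressing | not PD |
| 1 | not progressing | PD |
| 2 or more | progression | PD |

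The rules disagree only in the middle row.

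**Consequence in that row, by when the lesion appears.**

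1. *CR or PR already established.* Section 10.1.4.3 counts best response up to progression, so the category stands under both rules. Only the end of response differs. Under 10.1.4 it is the scan showing the single lesion. Under Section 10 it is a later event, or the participant is censored at the last disease evaluation. Scans are every 12 weeks, with a window of 1 week either side (Section 9). The next scan is therefore nominally 12 weeks later, and between 12 - 1 - 1 = 10 and 12 + 1 + 1 = 14 weeks with windows.
2. *Lesion seen before or at the scan that would establish or confirm the response.* Under 10.1.4 the participant is PD; under Section 10 he can still be CR or PR. The category changes, and under the 10.1.4 rule there is no response duration to measure.
3. *SD, with no later response.* SD against PD leaves him a non-responder either way in the Section 14.2 comparison, and he has no response duration.

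**Size.** The documents give no frequency for a single new bone lesion as the first sign of progression, so the number in cases 1 and 2 cannot be derived. Only the pool can be illustrated, using these inputs:

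- Planned enrollment: 66 (Section 14.1).
- Assumed share with assessable soft-tissue disease, from the phase I/II study in Section 2.1.1: 59/140 = 42.1%.
- Soft-tissue response rates in Section 2.1.1: 22% (phase I/II) and 29% (post-docetaxel phase III, enzalutamide arm).

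Results:

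- Participants with measurable disease: 66 x 0.421 = 27.8, about 28.
- Responders: 27.8 x 0.22 = 6.1 to 27.8 x 0.29 = 8.1, about 6 to 8.
- Arithmetic ceiling if all 66 had measurable disease: 66 x 0.22 = 14.5 to 66 x 0.29 = 19.1, about 15 to 19 responders.
- One participant moved from PR to PD (case 2): 1/28 = 3.6 percentage points of response rate, or 1/66 = 1.5 points at the ceiling.

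The last line is the effect of one hypothetical participant, not an expected effect.

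**The case against.** The best reply is that Section 10 already settles the matter. Its opening says that participants with measurable disease, the very group whose response is at issue, are assessed by RECIST 1.1 for soft tissue and by PCWG-2 for bone. It presents its list as the rules for progression in this study, and 10.1 is a subsection beneath it. On that reading the trial-specific rule governs the general RECIST text, and nobody is PD in a table while still properly on drug.

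This is a coherent reading and probably the intended one. It does not remove the conflict:

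- Section 10.1 is unqualified, and no text gives precedence.
- The new-lesion note names bone lesions, which would be unnecessary if bone lay outside 10.1.4.
- Section 10.1.2 admits certain bone lesions with a measurable soft-tissue component as target lesions, and Section 14.2 plans a duration of response for bone lesions. Bone is therefore within the response assessment.
- Someone following the tables literally would record PD.

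Three other parts of the reply stand in full. An established response keeps its category. A new bone lesion beside shrinking target lesions at the first scan is where the flare caveat is most likely to apply, which narrows case 2 further. And an average shift in weeks would be a poor measure of effect, because the plan uses Kaplan-Meier and one changed date need not move the median.

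**Conclusion.** The two rules contradict each other for exactly one unequivocal, non-flare new bone-scan lesion with no other progression, and the plan does not say which applies to response. The effect is minor. For an established CR or PR it is confined to the end of response: at least one 12-week interval, or an event turned into censoring. The category changes only when the lesion comes before or at the establishing or confirming scan. The number affected is unknown. The illustrative pool of 6 to 8 responders rests on carrying over the soft-tissue share and response rates of earlier trials.

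A reader might infer more than this, and the documents do not support it:

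- *That every participant with one new bone lesion has both his category and his end date at risk.* Cases 1 and 3 above show otherwise.
- *That treatment stopping, biopsy timing or the primary paired-biopsy analysis is in doubt.* Section 10 states the progression rules under which participants stay on treatment, and the study-duration text of Section 14.1 names PCWG-2 for radiographic progression. The primary analysis does not use response categories, and its sample size does not depend on them.

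The outputs that do depend on the rule are secondary and descriptive, or explicitly exploratory.

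**What to change.** In 10.1.4, with a footnote to both overall-response tables, and again in 10.1.5, state that:

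- new lesions seen on bone scan count as PD only under the Section 10 PCWG-2 rule (two or more new lesions), so a single new bone-scan lesion alone is not PD;
- new soft-tissue lesions, including measurable soft-tissue components of bone lesions on CT or MRI, remain under RECIST 1.1.

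The second statement is needed because 10.1.2 allows such components to be measured; a blanket statement that one new bone lesion is never PD would wrongly exclude them. Central review should be told to apply the same rule.

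The cost is two sentences and a footnote, with no extra scans or visits. The downside is that a few participants may be called PD later for duration of response.

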## 5.4 Duration of Therapy

Duration of therapy will depend on individual response, evidence of disease progression, and tolerance. In the absence of treatment delays due to AEs, treatment may continue until one of the following criteria:

- Symptomatic or radiographic disease progression
- Intercurrent illness that prevents further administration of treatment
- Unacceptable AE(s)
- Treatment emergent seizure
- Participant decided to withdraw from the study
- General or specific changes in the participant's condition render the participant unacceptable for further treatment in the opinion of the treated investigator.

Protocol therapy may be held for up to six weeks in the event of an AE and the participant may be restarted on therapy when the toxicity has resolved to  $\leq$  grade 1. In the event of therapy being held for more than six weeks, it is recommended that the participant come off protocol however the treating physician may obtain permission to continue on the protocol with permission of the PI, [REDACTED] if the treating physician feels it is in the participant's best interest.

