- l: For DFCI participants only, one bed position of quantitative SPECT/CT will be performed as an imaging substudy concurrently with the standard of care bone scans at baseline and at the time of the first two follow up standard of care bone scans. The field of view will be determined by the nuclear medicine physician depending on the location of the lesions on the planar images.
- m: Study agent is enzalutamide. Subjects will be continued on LHRH agonist/antagonist as prescribed. Subjects will begin taking study agent on Day 1/Cycle 1.
- n: AEs should be collected from the date informed consent is signed until 30 days after discontinuation from the study.
- o: Tumor biopsy must be performed prior to starting study medication. Participants will need to be screening and registered before having a biopsy. Friday should be avoided due to difficult of processing bone biopsies on the weekend. For DFCI participants, if the biopsy site (baseline and progression) is a pelvic bone both an aspirate and core biopsy will be obtained.
- p: Participants who stop the protocol therapy before receiving four cycles of enzalutamide will not be asked to undergo the second biopsy. The tumor biopsy at the end of the study can be done +/- 14 days of the determination of progression. Enzalutamide will be discontinued following completion of the second biopsy. Situations where the participant stops protocol therapy for reasons other than progression after receiving four cycles of enzalutamide should be discussed with the PI if it felt that the biopsy would not represent progressive disease.
- q: The End of Treatment Visit will be the visit at which it is determined that the patient will no longer be taking treatment given disease progression, toxicity, or other reason.
- r: Follow up Visits: Participants will be followed for up to 5 years post-study discontinuation or until death, whichever comes first. Participant follow up visits will be at the research clinic for the first 2 years of follow-up. Following the first 2 years, participant follow-up can be done via medical record review and/or by phone. Participants will be followed for subsequent lines of therapy, including line of agent, name of agent, and PSA kinetics following study drug discontinuation and correlate with response to study drug. This information will be updated every 6 months. The research team will collect this information during patient clinic visits, by phone, or via medical record review.

CONFIDENTIAL

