**Number of Subjects/Study Duration:**

We plan to enroll a total of 66 participants to obtain 40 evaluable participants. Assuming an accrual rate of 6 participants per month, enrollment will take 11 months. Participants will be treated with enzalutamide 160 mg orally per day. We will assess PSA at baseline and day 1 of each 28-day cycle until radiographic progression defined by PCWG2. Participants will continue on therapy until radiographic or symptomatic progression or taken off study for another reason.

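### Section 10 lists reasons for stopping treatment among the items that determine progression, and Section 14.1 does not require the second biopsy to be the one taken at progression

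*Combined protocol and SAP*

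**What the plan says.** Section 10 introduces a list with "The following will be used to determine progression in this study". The first two items define PSA progression and radiographic progression. The third reads "If any of the following criteria that are also described in Section 5.4 are met" and repeats all six criteria of Section 5.4. One of the six is symptomatic or radiographic progression. The other five are intercurrent illness, unacceptable adverse events, treatment-emergent seizure, withdrawal, and a change in condition that rules out further treatment.

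In Section 5.4 the same list has a different role: "treatment may continue until one of the following criteria".

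Section 14.1 limits the primary analysis to participants who had at least 2 cycles and who experienced progression. It compares paired biopsies with a paired t-test. It does not say when the second biopsy must have been taken.

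Sections 1 and 5 place that biopsy at progression. Section 5 and note p of the Study Calendar (Section 9) provide for a participant who "stops protocol therapy for reasons other than progression after receiving four cycles of enzalutamide": the case "should be discussed with the PI if it felt that the biopsy would not represent progressive disease".

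**The concern.** The primary analysis reads the change from baseline to second biopsy as evidence of resistance. A pair from a man who stopped for toxicity while the drug was still working is not a resistance pair, and it can pull the mean change toward zero. Two routes could bring such a pair into the primary set:

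1. Under the literal Section 10 list, a stop for an adverse event or withdrawal is itself progression, so the man meets the Section 14.1 condition.
2. Even with Section 10 corrected, a man biopsied at a toxicity stop who progresses later has experienced progression. Section 5.5 allows follow-up for up to 5 years. The Section 14.1 condition describes the man and not the biopsy, so his pair would still qualify.

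The literal list also affects time to progression (Section 10.1.6), where these stops would become events instead of censored observations.

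**Working it through.** **Comparing the sections.**

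- Section 10, sentence before the list: "Participants should not be taken off treatment until documented symptomatic progression or progression by imaging". Here progression is symptomatic or by imaging.
- Section 5.4: the same six criteria end therapy, and progression is only one of them.
- Section 5 and Section 9 note p: stops for reasons other than progression form a separate class.
- Section 9 note q: treatment ends when "it is determined that the patient will no longer be taking treatment given disease progression, toxicity, or other reason". Progression and toxicity are alternatives.
- Section 10.1.6: participants without progression are censored at their last disease evaluation. That cannot hold if withdrawal is progression.
- Section 14.1, Number of Subjects/Study Duration: "Participants will continue on therapy until radiographic or symptomatic progression or taken off study for another reason".

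The third item of the Section 10 list stands alone against all of these.

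**The plan's own figures.** Inputs from Section 14.1: n = 40 pairs, paired t-test, one-sided alpha 0.025. Power = P(T > t(0.975, n-1)), where T is noncentral t with n-1 degrees of freedom and noncentrality d√n, and d = mean change / SD.

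- d = 0.454 gives 0.800 and d = 0.526 gives 0.900, matching the table in Section 14.1.

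**Size of a possible dilution.** The number of pairs biopsied at a non-progression stop is not in the documents. Assume k = 2, 4 or 6 of 40. The upper value comes from the 16% rate of discontinuation for adverse events in the randomized trial described in Section 6.1.1: 0.16 × 40 = 6.4. Assume a true change of 30% (the level Section 14.1 calls biologically significant) in the other pairs, zero mean change in the k pairs, and a common SD.

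The expected mean change is 30 × (40 - k)/40, which is 28.5%, 27.0% or 25.5%.

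Power if the k pairs are kept was simulated with exactly k pairs at mean 0 and 40 - k at mean 30. Power if they are excluded uses the formula above with n = 40 - k and d = 30/SD.

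| SD | No such pairs | k = 2, kept / excluded | k = 4, kept / excluded | k = 6, kept / excluded |
|---|---|---|---|---|
| 60% | 0.869 | 0.830 / 0.851 | 0.787 / 0.831 | 0.734 / 0.808 |
| 50% | 0.959 | 0.937 / 0.950 | 0.910 / 0.938 | 0.874 / 0.924 |
| 40% | 0.996 | 0.992 / 0.995 | 0.984 / 0.992 | 0.971 / 0.989 |

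At an SD of 30% every value is 0.999 or more. At an SD of 60% with k = 3, power with the pairs kept is 0.81, so the crossing below 80% lies between 3 and 4 pairs.

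A closed-form check treats f = k/40 as a mixing share, with effect (1-f)d / √(1 + f(1-f)d²). For SD 60% and k = 4: d = 0.5, f = 0.1, effect = 0.45/√1.0225 = 0.445, power 0.784. This agrees with the simulated 0.787.

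**Sensitivity to the zero-change assumption (SD 60%, pairs kept, k = 2 / 4 / 6).**

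- Mean change +15% in those pairs: 0.854 / 0.832 / 0.812, the same as excluding them to within simulation error.
- Mean change -15%: 0.809 / 0.730 / 0.640.

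**The case against.** The strongest reply is that the documents already convey the rule. Sections 1 and 5 place the second biopsy at progression, Section 5 and note p send doubtful cases to the PI, Section 10.1 evaluates progression by RECIST 1.1, and Section 14.1 requires progression. The third item of the Section 10 list also looks like a misplaced fragment. It is an unfinished clause, it lacks the label and definition of the two items above it, it includes progression among its own criteria, and it cites the section on ending therapy. An analyst is unlikely to count a seizure as tumour progression.

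Most of this stands. The intent is clear, and the PI discussion is a real, if partial, safeguard. It does not remove the point. Section 10 is where an analyst would look for the definition, and the rule stated there is wrong. The PI discussion has no stated outcome, and nothing says how a biopsy taken anyway is analysed. The second route remains open whichever way the Section 10 list is read.

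The reply is also right about size. The range of 2 to 6 pairs is assumed, and its upper end is likely high. To contribute a pair, a man who stops for an adverse event must also have completed four cycles, been biopsied after any PI discussion, and given evaluable tissue. The -15% scenario has no basis in the documents.

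A reader might infer that the trial means to count withdrawals and toxicity stops as progression, or that the primary analysis is seriously underpowered. The documents support neither: the other sections contradict the first, and the table above does not bear out the second.

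**Conclusion.** The Section 10 list is wrong as written. It conflicts with Sections 5, 5.4, 9 (notes p and q), 10.1.6 and 14. Followed literally, it admits non-progression stops to the primary set and turns them into time-to-progression events. Separately, Section 14.1 does not tie the second biopsy to progression. Exclusion of such pairs is clearly intended but nowhere stated.

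The effect is probably small. Assuming zero mean change in 2 to 6 of 40 pairs and a true 30% change elsewhere, power falls below 80% only at the largest tabulated SD (60%) with about 4 or more such pairs. At an SD of 50% or less it stays at 87% or above. These figures rest on an assumed count and an assumed change, neither of which the documents supply. The main reason to correct the text is that membership of the primary set should not depend on which section is read. The correction should be made; confidence is medium.

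**What to change.** **Section 10.** Keep PSA, radiographic and symptomatic progression in the progression list. Move the other five items under a separate heading, *Other reasons for stopping treatment*.

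**Section 14.1.** Add: *The primary paired analysis uses second biopsies taken at progression as defined in Section 10; second biopsies taken at a stop without progression are summarized separately.*

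Two tighter rules should be avoided. A hard 14-day limit in the analysis rule would leave a progression biopsy taken a few days late in neither group. Limiting pairs to symptomatic or radiographic progression would drop men with PSA progression, which narrows the present Section 14.1 condition and is debatable.

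**Cost.** Text changes only, with no new visit or biopsy. A few pairs may leave the primary set; with 34 pairs (40 - 6), power for a 30% change at an SD of 60% is still about 81%. Section 12.1.2 names the case report forms but not their fields, so the sponsor should confirm that biopsy date, progression date and reason for stopping are captured.
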